9.6.2 Statistical Methods for Safety Analyses

Safety and tolerability will be assessed by clinical review of all relevant parameters, including AEs, laboratory tests, and vital signs. Safety summaries will be pooled across all indications. The additional safety analyses for each tumor type might be conducted if desired and will be documented in the sSAP. The safety analysis population will be used for the analysis of safety data. TEAE is defined as all AEs from the treatment start date until 30 days after last dose (30 days for SAE). The incidence of TEAEs and SAEs will be summarized by system organ class and preferred term. Continuous measures such as changes from baseline in laboratory test data, vital signs, 12-lead ECGs, cardiac function by echocardiography or MUGA scan, urine dipstick, and Lansky play scores or KPS scores will be summarized using descriptive statistics (mean, standard deviation, etc.) for baseline, on-treatment, and change-from-baseline values.

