6.3.2 Stratification

No stratification based on age, sex, or other characteristics will be used in this study.

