6.6.1 Blood Pressure

For children, BP varies by the sex and age of the child and it is closely related to height and weight. BP will be assessed in terms of percentile for sex, age, and height/length. Guidelines to sex, age, and height/length-specific percentiles of BP are provided in Appendix 11 and Appendix 12. BP that is consistently above the 95th percentile based on sex, age, and height/length (or BP $\geq 140/90$ mm Hg for participants 18 to 21 years old) requires further evaluation. A referral to a cardiologist is recommended for participants who develop hypertension during the study. Ideally, cardiovascular assessments and the management of hypertension should be supervised by a cardiologist. Exercise, excitement, coughing, crying, and struggling may raise the systolic pressure of children as much as 40 to 50 mm Hg greater than their usual level. Variability in BP in children of approximately the same age and body build should be expected, and serial measurements should always be obtained when evaluating a participant with hypertension. **BP values for the management of hypertension for participants 18 to 21 years old are included in parentheses in Section 6.6.2.**

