8.3.2 Dental Examination

Information from studies in animals suggest that there is a risk of delayed tooth formation and/or physical growth and development. Therefore, dental examinations are being performed to evaluate participants for potential anomalies in tooth formation and eruption schedule.

Dental examination by a dentist or qualified dental professional should be conducted per local institutional guidelines during screening and thereafter per local standard of care, but no less than annually, and at EOT. The baseline dental examination can occur up to 4 weeks after the first dose of study intervention. If the most recent dental examination is within 6 months prior to the EOT visit, the dental examination is not required.

Post-screening dental examinations are not required for participants for whom permanent teeth (excluding third molars) are evaluated to be fully erupted at screening.

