8.3.3 Vital Signs

Vital sign measurements (ie, systolic and diastolic BP [mm Hg], pulse rate [beats per minute], respiratory rate [per minute], body temperature [in centigrade]), weight [kg], and height [cm]) will be obtained at the visits designated in the SoA (Section 1.3) by a validated method.

- BP and heart rate will be measured after the participant has been resting for approximately 5 minutes. All BP measurements should be performed on the same arm, preferably by the same person.
- Only 1 BP measurement is needed for participants with systolic BP <95th percentile (BP <140 mm Hg) and diastolic BP <95th percentile (BP <90 mm Hg). If the participant's first BP measurement of the current assessment is elevated (systolic BP \geq 95th percentile [BP \geq 140 mm Hg] or diastolic BP \geq 95th percentile [BP \geq 90 mm Hg]), the BP measurement should be repeated at least 5 minutes later. The mean value of 2 measurements at least 5 minutes apart is defined as 1 BP assessment. If the BP assessment (ie, the mean of the 2 BP measurements obtained at least 5 minutes apart) is elevated (systolic BP \geq 95th percentile [BP \geq 140 mm Hg] or diastolic BP \geq 95th percentile [BP \geq 90 mm Hg]), a confirmatory assessment should be obtained at least 30 minutes later by performing 2 measurements (at least 5 minutes apart) to yield a mean value.
- At the C1D8 contact (clinic or telephone visit), and if required between clinic visits, participants will have BP measured. If the participant does not return to the study site for this BP measurement, BP may be measured, for example, at home or at a local pharmacy, and the results will be reviewed with the investigator or designee. The investigator/site may provide a diary as a tool to aid the participant in collecting BP evaluations between clinic visits. The sponsor will not provide diaries to the site. If BP result raises concerns, the investigator may require additional follow-up, including an on-site BP re-test, or other clinically appropriate intervention(s).

- Height and weight will be assessed at C1D1 and thereafter on Day 1 of every cycle during treatment, and at the EOT Visit. Height will also be monitored every 3 months in efficacy and survival follow-up until puberty has completed. Telephone contact is acceptable for height assessment if clinic visits are not possible at post-treatment visits after the 30-day safety FU.

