9.10 Subgroup Analyses

No subgroup analysis is planned.

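### No age- and sex-standardised summary is planned for height and weight, so a pooled mean change cannot separate slowed growth from normal growth and age mix

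*Combined protocol and SAP*

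**What the plan says.** Height appears among the safety endpoints in Section 9.4.2, next to closure of the proximal tibial plates. Section 8.3.3 treats it as a vital sign recorded in plain units: "weight [kg], and height [cm]) will be obtained at the visits designated in the SoA". The Schedule of Activities row for vital signs also includes height and weight. Height is measured on Day 1 of every cycle and at end of treatment, then every 3 months in efficacy and survival follow-up until puberty is complete.

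For analysis, Section 9.6.2 covers "Continuous measures such as changes from baseline in laboratory test data, vital signs, 12-lead ECGs, cardiac function by echocardiography or MUGA scan" and further items, to be "summarized using descriptive statistics (mean, standard deviation, etc.) for baseline, on-treatment, and change-from-baseline values". It adds: "Safety summaries will be pooled across all indications". Section 9.10 states: "No subgroup analysis is planned". Section 6.3.2 states: "No stratification based on age, sex, or other characteristics will be used in this study". Enrolment runs from age 2 to 21 (Section 5), with no control group (Section 1.1).

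On growth, Section 8.3.2 reports that animal studies suggest "there is a risk of delayed tooth formation and/or physical growth and development". For blood pressure, Section 6.6.1 says "BP will be assessed in terms of percentile for sex, age, and height/length", but no percentile is carried into Section 9.

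**The concern.** Children gain height and weight whether or not a drug affects their growth, and participants with closed growth plates do not get taller. Without a control arm, the expected gain has to come from an age- and sex-specific reference. Section 9 names none, so the reader of a mean change in cm has nothing to set it against. The mean stays positive even if growth is much reduced, and it moves with the proportion of young children enrolled. The right data are collected for a named safety endpoint, but the stated summary cannot show whether growth slowed. The wording also covers only baseline, on-treatment and change values, so the post-treatment heights have no stated summary at all.

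**Working it through.** **Figures in the plan.** No target, effect size or precision for height, weight or blood pressure is visible, so there is none to reproduce. The nearest printed numbers are the percentile multipliers under Appendices 11 and 12. The normal quantiles at 0.90, 0.95 and 0.99 are 1.282, 1.645 and 2.326, which agree with them.

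**Does Section 9.6.2 reach height?** Sections 8.3.3 and 1.3 place height and weight inside vital signs, and 9.6.2 summarises vital signs. Section 9.4.2 lists height apart from vital signs, and 9.6.2 does not repeat it. Either height gets an unstandardised mean change or it has no stated method. Neither gives a standardised summary.

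**Height illustration.** Assumed velocities in cm/year (not in the documents), interpolated linearly between ages:

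| Age | 2 | 3 | 4 | 6 | 10 | 12 | 13 | 14 | 15 | 16 | 17 | 18 | 21 |
|---|---|---|---|---|---|---|---|---|---|---|---|---|---|
| Low | 7 | 6.5 | 6 | 5 | 4.5 | 5.5 | 5.5 | 4 | 2 | 1 | 0.5 | 0 | 0 |
| Mid | 8.5 | 8 | 7 | 6 | 5.5 | 7 | 7.5 | 6 | 4 | 2 | 1 | 0.3 | 0 |
| High | 10 | 9 | 8 | 7 | 6 | 8 | 9 | 8 | 6 | 3.5 | 2 | 0.5 | 0 |

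Ages are assumed uniform from 2 to 21. Pooled mean change = mean velocity × weeks/52, and halved growth is half of that. For the mid profile, the area under the velocity curve is 88.85 cm over 19 years, a mean of 4.68 cm/year; 4.68 × 48/52 = 4.32 cm. The 48 weeks are the 12 cycles of 28 days in Section 4.1.

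| Profile | Weeks | Normal (cm) | Halved (cm) | SD from age alone (cm) |
|---|---|---|---|---|
| Low | 16 | +1.11 | +0.56 | 0.71 |
| Mid | 16 | +1.44 | +0.72 | 0.84 |
| High | 16 | +1.72 | +0.86 | 0.93 |
| Low | 48 | +3.34 | +1.67 | 2.14 |
| Mid | 48 | +4.32 | +2.16 | 2.51 |
| High | 48 | +5.17 | +2.59 | 2.79 |

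**Age mix.** In the mid profile at 48 weeks, normal growth averages 5.93 cm below age 12 and 2.52 cm from age 12. With 70% under 12 the mean is 0.7 × 5.93 + 0.3 × 2.52 = 4.91 cm. With 30% it is 0.3 × 5.93 + 0.7 × 2.52 = 3.54 cm. No drug effect is involved. Children aged 2 to 11 growing at half speed average +2.97 cm, more than normally growing participants aged 12 to 21.

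**The same loss as a z-score.** Expected change is about 0 with normal growth. With growth halved it is −(0.5 × velocity × weeks/52)/SD, where the height SD for age is assumed to be 4 to 7 cm. At 48 weeks:

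| Velocity (cm/year) | Raw change (cm) | z change, SD 7 to SD 4 |
|---|---|---|
| 4 | +1.85 | −0.26 to −0.46 |
| 6 | +2.77 | −0.40 to −0.69 |
| 8 | +3.69 | −0.53 to −0.92 |

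At 16 weeks the loss is 0.62 cm (4 cm/year) to 1.23 cm (8 cm/year), so z falls by 0.62/7 = 0.09 to 1.23/4 = 0.31.

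**Blood pressure, from Appendices 11 and 12 (50th height percentile).** Median systolic pressure rises from 88 to 118 mm Hg in boys between ages 2 and 17, 30/15 = 2.0 per year, and from 88 to 111 in girls, 23/15 = 1.5 per year. The implied SD at age 17 in boys is (143 − 118)/2.326 = 10.7. Drift over 48 weeks is 2.0 × 48/52 = 1.8 mm Hg, small against that SD. Levels are another matter: 113 mm Hg is the 99th percentile for a boy of 2, while at 17 it gives z = (113 − 118)/10.7 = −0.47, about the 32nd percentile.

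**The case against.** Several points on the other side stand.

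- **Raw and pooled over ages are not the plan's words.** They follow from the recorded units, pooling across indications, the absence of subgroup analyses and the absence of any standardised score. A reader might infer that 9.6.2 definitely prescribes raw height change. Because 9.4.2 lists height apart from vital signs and the list in 9.6.2 is open-ended, the documents support only the statement that no standardised summary is specified.
- **The reason for measuring height.** A reader might infer that height is an endpoint because of the animal findings. Section 8.3.2 offers those findings as the reason for dental examinations; the link to height is plausible but not stated.
- **Other monitoring.** A reader might infer that growth harm would pass as no harm. Tibial growth-plate x-rays, Tanner staging, clinical review and the data monitoring committee all bear on growth or safety, so the signal is not wholly lost. Section 9.6.2 gives no summary method for the x-ray or Tanner data either.
- **Short exposure.** Treatment stops at progression, and median PFS in the cited osteosarcoma cohort was 3.0 months (Section 2.2.1.2). The 16-week figures may be closer to what is seen than the 48-week ones.
- **Attribution.** Prior craniospinal radiotherapy is permitted after a washout (Section 5.1). A z-score removes expected growth but not such confounding.
- **Blood pressure.** A reader might extend the masking argument to it. Change is within participant and drifts little with age, and hypertension is CTCAE-graded from measured values (Section 6.6.2). Only the pooled levels are hard to interpret.

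None of this supplies the missing reference for height and weight.

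**Conclusion.** The point holds for height and, by the same reasoning, for weight. The plan specifies no summary that allows for age and sex, and a mean change in cm or kg in this single-arm population cannot distinguish slowed growth from normal growth and age mix. On the assumed velocities, halving growth in everyone leaves a 48-week mean of +1.7 to +2.6 cm, against +3.3 to +5.2 cm with normal growth. Age mix alone moves the mid-profile mean by 4.91 − 3.54 = 1.37 cm.

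The sizes rest on assumed velocities, a uniform age distribution and an assumed height SD. The direction is the same over the range shown. The documents do not support claims that growth toxicity would go undetected or that blood pressure change is masked by growth. This is a descriptive secondary safety summary, well worth improving because the change is cheap; the primary efficacy analysis is unaffected.

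**What to change.** In Section 9.6.2, or in the sSAP, which Section 9 allows for non-confirmatory analyses:

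- Summarise height, and secondarily weight, as age- and sex-standardised z-scores with change from baseline.
- Name a height-for-age and a weight-for-age reference. Appendix 13 does not provide them: it holds BMI-for-age charts labelled 2 to 20 years. State how participants beyond the reference's age range are handled, since enrolment goes to 21.
- Present height separately for participants with open growth plates or incomplete puberty at baseline.
- Include the post-treatment heights collected every 3 months.
- State that height is analysed under these rules whether or not it is counted as a vital sign, so that 9.4.2, 8.3.3 and 9.6.2 agree.

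As a side improvement, report blood pressure for participants under 18 as shifts across the 95th and 99th percentiles of Appendices 11 and 12.

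The cost is a few derived variables and the choice of a reference. Age, sex, height, weight, Tanner stage and growth-plate status are already collected, so no visit or procedure is added. The report should say that a z-score shift without a control arm cannot be attributed to the drug alone.

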6.6 Dose Modification

Lenvatinib dose reduction and interruption for participants who experience lenvatinib-related toxicity will be in accordance with the dose modifications described in [Table 3](#). AEs will be graded using CTCAE v5.0.

Asymptomatic laboratory abnormalities, including Grade ≥ 3 abnormalities (eg, elevations of amylase and lipase) that are not considered clinically relevant by the investigator should be managed per institutional guidelines; continuation of treatment should be discussed with the Sponsor.

Dose reductions will occur in succession based on the previous dose. Each reduction is a 20% reduction from the previous dose. Once the dose has been reduced, it cannot be increased at a later date, unless the dose has been mistakenly decreased; in this situation, Sponsor's approval is required to increase the dose. An interruption of lenvatinib >28 days will require consultation between the investigator and the Sponsor and written documentation of the collaborative decision on participant management.

Table 3 Criteria for Temporary Discontinuation of Study Drug, Dose Reduction, and Resumption of Treatment

Dose Modification Guidelines for Lenvatinib-Related Toxicity		
Treatment-Related Toxicity^{a,b}	Management	Dose Adjustment
Grade 1 or Tolerable Grade 2		
	Continue treatment	No change
Intolerable Grade 2^{c, d} or Grade 3^e		
First occurrence	Interrupt lenvatinib until resolved to Grade 0-1 or tolerable Grade 2	11.2 mg/m ² (or 20% reduction of the starting dose) orally QD (1-level reduction)
Second occurrence (same toxicity or new toxicity)	Interrupt lenvatinib until resolved to Grade 0-1 or tolerable Grade 2	9.0 mg/m ² (or 20% reduction of the previous dose) orally QD (1-level reduction)
Third occurrence (same toxicity or new toxicity)	Interrupt lenvatinib until resolved to Grade 0-1 or tolerable Grade 2	7.2 mg/m ² (or 20% reduction of the previous dose) orally QD (1-level reduction)
Fourth occurrence (same toxicity or new toxicity)	Interrupt lenvatinib	Discuss with Sponsor
Grade 4^f: Discontinue Study Treatment		
Abbreviations: BMI = body mass index; CTC = Common Toxicity Criteria; CTCAE = Common Terminology Criteria for Adverse Events; QD = once daily. Note: For grading, see CTCAE version 5.0. Collect all CTC grades of adverse events, decreasing and increasing grade.		

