6.6.8 Management of Hypocalcemia

Serum calcium should be monitored monthly per the SoA (Table 1). Corrected serum calcium should be used to assess the grade of hypocalcemia per CTCAE v5.0, using the following formula:

$$\text{Corrected calcium} = (4 - \text{serum albumin in g/dL}) \times 0.8 + \text{serum calcium}$$

The formula is not applicable when serum albumin concentration is normal (>4 g/dL); in such situations, the total (uncorrected) serum calcium should be used instead.

Hypocalcemia should be treated per institutional guidelines (eg, using appropriate calcium, magnesium, and vitamin D supplementation) until resolution.

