8.3.6.1 Hematology and Clinical Chemistry

Hematology (complete blood count with differential) and clinical chemistry will be performed within 7 days prior to the first dose of study intervention and do not need to be repeated at C1D1 (unless clinically indicated) and within 72 hours prior to all subsequent visits (Appendix 2). All clinical laboratory tests during the study will be performed by local laboratories. All hematology, blood chemistry (including pregnancy test, as applicable), and urinalysis samples are to be obtained prior to study drug administration and sent to the local laboratory on the day of collection, unless otherwise instructed.

All hematology, blood chemistry (including pregnancy test, as applicable), and urinalysis samples are to be obtained and assessed and the results reviewed prior to study drug

administration on C1D1 and within 72 hours prior to the visit for all subsequent cycles. If \geq Grade 3 hematologic or clinical chemistry toxicity, repeat laboratory test and AEs assessment at least every 3 days (until improvement to $<$ Grade 3). Refer to [Table 3](#) for the management of lenvatinib-related toxicity.

Electrolytes such as potassium, calcium, and magnesium should be monitored and abnormalities, when considered clinically significant, should be corrected in all participants before starting treatment.

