8.4.7 Events of Clinical Interest

Selected nonserious and SAEs are also known as ECIs and must be reported to the Sponsor.

Events of clinical interest for this study include:

An elevated AST or ALT lab value that is greater than or equal to 3X the upper limit of normal and an elevated total bilirubin lab value that is greater than or equal to 2X the upper limit of normal and, at the same time, an alkaline phosphatase lab value that is less than 2X the upper limit of normal, as determined by way of protocol-specified laboratory testing or unscheduled laboratory testing.*

*Note: These criteria are based upon available regulatory guidance documents. The purpose of the criteria is to specify a threshold of abnormal hepatic tests that may require an additional evaluation for an underlying etiology. The study site guidance for assessment and follow up of these criteria can be found in the Investigator Study File Binder (or equivalent).

Lenvatinib overdose is not considered an ECI.

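### Section 9.6.2 plans no count of laboratory abnormalities by CTCAE grade or multiple of ULN, so some Grade 3 or higher values would go uncounted

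*Combined protocol and SAP*

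**What the plan says.** Section 9.6.2 gives laboratory data one method, shared with vital signs, ECGs, cardiac function, dipstick results and performance scores. "Continuous measures such as changes from baseline in laboratory test data" and the other listed measures "will be summarized using descriptive statistics (mean, standard deviation, etc.) for baseline, on-treatment, and change-from-baseline values". The summary in Section 9.1 repeats this and presents Sections 9.1 to 9.12 as the full plan. On pooling, Section 9.6.2 says "Safety summaries will be pooled across all indications", and Section 9.10 says "No subgroup analysis is planned". TEAEs and SAEs are tabulated by system organ class and preferred term, with no breakdown by grade.

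Elsewhere the protocol judges laboratory results against limits and grades:

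- Section 8.3.6.1: "All clinical laboratory tests during the study will be performed by local laboratories". The Schedule of Activities allows thyroid tests to go to a central laboratory.
- Section 6.6 and Table 3 work by CTCAE v5.0 grade and foresee "Asymptomatic laboratory abnormalities, including Grade ≥ 3 abnormalities (eg, elevations of amylase and lipase) that are not considered clinically relevant by the investigator".
- Section 6.6.8: "Corrected serum calcium should be used to assess the grade of hypocalcemia per CTCAE v5.0".
- Section 8.4.7 defines the liver event of clinical interest (ECI). It begins with "An elevated AST or ALT lab value that is greater than or equal to 3X the upper limit of normal" and also requires bilirubin at least 2×ULN together with alkaline phosphatase below 2×ULN.
- Section 10.3.2 treats an abnormal laboratory result as an AE when the investigator considers it clinically significant.

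**The concern.** Clinical laboratory values are a named safety endpoint (Sections 3 and 9.4.2). The safety question about them is how many participants crossed a limit, how far, and from what starting point. A pooled mean and standard deviation do not answer that. With no control arm, a count by grade is also the form most easily set beside other lenvatinib experience.

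The protocol acts on grades and ULN multiples for dose changes, repeat testing and liver reporting, but the analysis does not count on those scales. If the only counted route is the AE table, the count depends on each investigator's judgement of clinical significance. The issue is not remote: Section 4.3 lists a Grade 3 ALT increase among the three dose-limiting toxicities at 14 mg/m², the level used here. That case was recorded as an event. It is cited only to show that such values occur.

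**Working it through.** The documents state no figure on this point, so there is nothing to reproduce. The sample size text and the efficacy interim text are redacted, but neither concerns laboratory summaries. The check is to follow each kind of abnormal result to the planned output that would count it.

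1. **Judged clinically significant.** It is an AE (10.3.2) and goes in the AE section of the CRF (8.3.6). It is counted under a preferred term, but not by grade.
2. **Meets the combined liver criterion (8.4.7).** It is a reportable ECI, due to the Sponsor within 24 hours as potential drug-induced liver injury (Table 4). Section 9 plans no ECI table.
3. **Isolated ALT or AST at or above 3×ULN, without the bilirubin and alkaline phosphatase conditions.** It is not an ECI. If it is not recorded as an AE, it enters the continuous summaries only.
4. **Asymptomatic Grade 3 or higher value judged not clinically relevant (6.6; Table 3, footnote e).** If it is therefore not recorded as an AE, it enters the continuous summaries only.
5. **Low calcium.** It is graded on the albumin-corrected value (6.6.8). Section 9 does not say which calcium value is summarised and names no count by grade.

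Routes 3 and 4 are the gap. Route 5 falls into it when the result is not an AE.

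How likely are Grade 3 or higher values at all? Inputs: N = 36, the planned minimum, and N = 150, the estimated upper figure (both in 4.1); an assumed true rate p for one test of 2%, 5% or 10%. The documents give no such rate.

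P(at least one) = 1 − (1 − p)^N

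| p (assumed) | N = 36 | N = 150 |
|---|---|---|
| 2% | 1 − 0.98^36 = 0.517 | 1 − 0.98^150 = 0.952 |
| 5% | 1 − 0.95^36 = 0.842 | above 0.99 |
| 10% | 1 − 0.90^36 = 0.977 | above 0.99 |

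Section 4.4 reports that two cohorts were not expanded and that enrollment into a third was discontinued, so the N = 150 column is an outer bound. The table gives the chance that any such value occurs. It does not give the chance that one goes unrecorded as an AE, which the documents do not allow us to estimate.

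**The case against.** The best defence is that the gap is narrow.

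- Grade 3 or higher hematology or chemistry toxicity triggers repeat tests and an AE assessment at least every 3 days (8.3.6.1).
- Clinically relevant changes go to the AE data (8.3.6), and Table 3 asks for all grades of AEs to be collected.
- The combined liver signal is captured on a ULN scale without depending on a judgement of significance (8.4.7).
- Sections 9.4.2 and 9.6.2 provide for clinical review of laboratory results, and an external DMC reviews safety data (9.7.1).
- A supplemental SAP could add tables.

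Most of this stands, and it limits the point to routes 3 to 5. It does not close them. Clinical review and DMC review are not tabulations. Collecting grades of AEs does not reach values that are not AEs. For safety, Section 9.6.2 mentions the supplemental SAP only for optional analyses by tumor type.

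A reader might go further in three ways that the text does not support:

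- *That laboratory data are summarised only as raw mean change.* Baseline and on-treatment values and the standard deviation are also planned, the list of statistics is open-ended and could include extremes, and the plan is silent on normalisation rather than ruling it out.
- *That the abnormal values appear in no planned table.* They enter the continuous summaries. What is missing is their count as abnormalities.
- *That the age-specific creatinine limits measure the bias from pooling ages.* They are eligibility ceilings. Change from baseline is within participant, so differences in level largely cancel.

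**Conclusion.** The point holds in a limited form. As written, Section 9.6.2 describes laboratory data on a continuous scale and counts no one by CTCAE grade or ULN multiple. Grade 3 or higher values judged not clinically relevant, and isolated ALT or AST elevations outside the combined rule that are not recorded as AEs, would not be counted as abnormalities in any planned table. It does not follow that hepatotoxicity, hypocalcemia or renal toxicity in general would go unseen.

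The number affected cannot be derived. The 52% to 98% chance of at least one Grade 3 or higher value for a test at N = 36 rests on assumed rates of 2% to 10% and describes occurrence, not omission. The conclusion also assumes that no unseen supplemental plan adds these tables; the documents commit to none. The change is worth making because a safety endpoint should be counted on the scales the protocol itself uses.

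**What to change.** Keep the descriptive statistics. Add to Section 9.6.2, for the Safety Analysis Set and whether or not the value was reported as an AE:

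- **(a) Shift tables** from baseline to worst post-baseline CTCAE v5.0 grade, with n/N at Grade 3 or higher, using each laboratory's own limits and calcium corrected as in Section 6.6.8. Unscheduled repeat results should be included.
- **(b) Liver counts:** participants with ALT or AST at least 3×ULN, with bilirubin at least 2×ULN, and meeting the combined Section 8.4.7 criterion.

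One related text should be settled before (a) is programmed. Section 9.5.2 requires a C1D1 baseline for change values, while Section 8.3.6.1 lets C1D1 tests be omitted when they were done within the 7 days before first dose. Read literally, this could drop participants from change and shift summaries, so the two should be reconciled.

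The cost is SAP wording and a small amount of standard programming, with no new samples. Local limits are already needed for eligibility (5.1) and the ECI rule; the team should confirm that they are held in the database. No dose or clinical rule changes.
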